8.1.3 Storage and preparation

DCs used in the vaccine will be suspended in 5% human serum albumin (HSA) and delivered to the clinic for administration. For preparation of the vaccines, the labeled vials of cryopreserved α DC1 are removed from storage in liquid nitrogen and quickly thawed in a 37°C water bath. After 3 washes in sterile medium, thawed α DC1 will be suspended in saline with 5% human serum albumin (HSA) and placed in sterile syringes for administration to the patient. Each syringe will be labeled with a custom-designed label, identifying the patient and the vaccine.

Intranodal and intradermal vaccines will be delivered as single injections.

8.1.4 Supplier

The DC vaccine will be prepared by the cGMP facility of the University of Pittsburgh Cancer Institute, in a process analogous to the vaccine for colorectal cancer patients covered by the existing BB-IND 13,234.

8.2 Celecoxib

A sulfa non-steroidal anti-inflammatory drug (NSAID) used in the treatment of osteoarthritis, rheumatoid arthritis, acute pain, painful menstruation and menstrual symptoms, and to reduce numbers of colon and rectum polyps in patients with familial adenomatous polyposis.

8.2.1 Other names

Celebrex, Celebra, or Onsenal (*commercially available*)

8.2.2 Formulation and packaging

Celecoxib as capsules in the following dosages: 100 mg, 200 mg, and 400 mg.

8.2.3 Preparing and dispensing

Externally prepared and dispensed per treating physician prescription. Drug storage and accountability

Store at room temperature at 77 °F (25 °C) away from light and moisture. Brief storage between 59-86 °F (15-30 °C) is permitted.

8.3 Interferon- α 2b

An antiviral drug approved around the world for the treatment of chronic hepatitis C, chronic hepatitis B, hairy cell leukemia, chronic myelogenous leukemia, multiple myeloma, follicular lymphoma, carcinoid tumor, and malignant melanoma.

8.3.1 Other names

Interferon- α 2b, Intron® A, IFN- α 2b, IFN α , IFN, NSC #377523 (*commercially available*)

8.3.2 Formulation and packaging

50 MU/mL, lyophilized powder, which must be reconstituted prior to administration.

Vial size: 10 MU/vial

Diluent: Compatible with normal saline, Ringer's injection, lactated Ringer's, and 5% sodium bicarbonate injection. IFN α should be reconstituted with 1 mL to reach a final concentration of 10:1. IV dose should be diluted in sodium chloride 0.9%/100 mL (100,000 U/mL) and given over 20 minutes. The final concentration of INTRON A should not be less than 10 million IU/100 mL

Source: Schering Plough Corp.

8.3.3 Preparing and dispensing

The lyophilized product is reconstituted as directed by the manufacturer. Investigational Drug Services will prepare and dispense.

For IV injection, it is recommended that IFN α be administered as a 100,000 U/mL solution to minimize adsorption of the drug to glass and plastic containers.

8.3.4 Concomitant medications

Interactions between IFN α and other drugs have not been fully evaluated. Caution should be exercised when administering IFN α therapy in combination with other potentially myelosuppressive agents such as zidovudine. Concomitant use of IFN α and theophylline decreases theophylline clearance, resulting in a 100% increase in serum theophylline levels. Concomitant IFN α and REBETOL (Ribavirin) use is contraindicated.

For more information on concomitant medications reference the Investigator's Brochure or package insert.

8.4 Rintatolimod (poly IC analog)

A substituted double stranded polyribonucleic acid (polyI:polyC₁₂U), rintatolimod preserves activity of polyIC with a much improved systemic toxicity profile. The product has been studied extensively for use as a vaccine adjuvant and for its direct antiviral activity, as well in several cancer studies as a monotherapy, but most extensively in chronic fatigue syndrome (CFS).

8.4.1 Other names

PolyIC₁₂U, Ampligen®, poly I: polyC₁₂U; Polyinosinic:polycytidylic-polyuridylic acid; polyriboinosinic/polyribocytidylic (uridylic) acid; supplied by Hemispherx Biopharma, Inc.

8.4.2 Formulation and packaging

Rintatolimod is supplied as a liquid solution in glass bottles containing 200 mg per 80 mL. Rintatolimod is a colorless solution containing 2.5 mg/mL in physiological salts (0.15 M NaCl, 0.01 M phosphate, 0.001 M Mg⁺⁺). The product does not contain preservatives or antioxidants.

8.4.3 Preparing and dispensing

A vial of rintatolimod is suitable for direct IV infusion. Investigational Drug Services will prepare and dispense. Each vial should be taken from the refrigerator and allowed to equilibrate to room temperature.

8.4.4 Drug storage and accountability

Rintatolimod should be stored at 2 to 8°C, but should be infused at room temperature. Used vials

should be accounted for and destroyed according to institutional procedure.

9. CORRELATIVE STUDIES

At indicated time points (see the study calendar, Section 10) up to 60 cc of peripheral blood will be collected and cryopreserved for potential correlative studies. For additional correlative studies, we may cryopreserve the available portions of the harvested tumors, not used for the preparation of autologous vaccines. The exact scope of the correlative studies will depend on the clinical outcomes and available funding, but may include:

- Changes in circulating subsets of immune cells (flow cytometry).
- Changes in serum immune mediators, cytokines, chemokines (Luminex, ELISAs).
- Changes in gene expression of blood cells (mRNA/Taqman assays).
- Changes in the frequencies and activity of tumor-reactive cells (ELISPOTs and ELISAs)

TTP may be correlated with the changes in the blood samples from the treated subjects. For subjects who will need palliative surgery or will demonstrate clinical response and will have accessible tumor tissue, we may obtain tumor material to analyze tumor-infiltrating CD8⁺ T cells in the resected metastatic CRC lesions and local expression of chemokines and other inflammatory mediators. This is measured as the ratio between the CD8 (or other gene) mRNA message and the expression of the housekeeping gene HPRT, in situ hybridization [ISH], and Immunohistochemistry/immunofluorescence [ICH/IF]. Examples of additional relevant parameters include total numbers of infiltrating T cells, their CD4/CD8 ratios, frequencies of FoxP3 cells, and the expression of chemokine receptors on CD4⁺ and CD8⁺ T cells (CXCR3, CCR5, CCR4, CCR6, and CXCR4). Using ISH, IF, and Taqman, we may also evaluate the local expression of T_{eff}-attracting chemokines: CCR5, CXCL9, and CXCL10 and CXCL11, and MDSC/T_{reg}-attracting chemokines: CCL22 and CXCL12. Similar assays may also be performed on any available pre-treatment tumors (if such material will remain after preparation of vaccines).

These potential correlative studies may allow us to determine if any blood- or tumor-associated markers are predictive of response to treatment and thus may be used as prospective inclusion criteria or assist us in prospective decisions regarding continuation of treatment in the individual patients. They may also facilitate development of additional therapies.

Any biological samples (from tissue, leukapheresis, blood draws, etc.) not needed for this research study will be de-identified and may be used for additional cancer research outside of this clinical trial.

10. STUDY CALENDAR

Baseline/screening evaluations will be conducted within 14 days and imaging will be conducted within 28 days of leukapheresis.

There is a window of ± 1 week available for scheduling treatment and/or procedures at the discretion of the Investigator/Sub-investigator. This applies also if a course is missed or a subject's treatment and/or testing day(s) need to be rescheduled due to the subject's inability to comply with the study calendar (i.e., hospitalizations, business, vacation plans, travel from long distances for study treatment, in advance of the scheduled date to allow ready access to the result(s), reduce financial burden on the subject [i.e. non-UPMC insurance coverage] or reduce travel inconvenience, illness, transportation issues, holidays, family emergencies, etc.).

Parameter	Eligibility	Surgery	Screening	Week 1* (Priming)	Week 4* (Booster Cycle 1)	Week 8* (Booster Cycle 2)	Week 12* (Booster Cycle 3)	Off treatment visit ⁹
Informed Consent	X							
History and Physical Exam ¹			X	X	X	X	X	
Vital Signs ²			X	X	X	X	X	
Adverse Event/Con Meds ¹⁰			X	X	X	X	X	X
ECOG Performance Status			X	X	X	X	X	
CEA			X					X
Urine pregnancy test ³			X	X ³				
CT or MR imaging (scheduled as clinically indicated)			X ⁸			X		X
CBC, platelets, differential ⁷			X	X	X	X	X	
Chemistries ^{4,7}			X	X	X	X	X	
Leukapheresis			X					
α DC1 vaccine				X	Monday	Monday	Monday	
Chemokine modulation					Tues-Fri	Tue-Fri	Tue-Fri	
Celecoxib ⁵				X	M-F	M-F	M-F	
Blood (60 cc) in vitro assays ⁶				X	X	X	X	
Tissue collection		X						

*. The indicated weeks represent "target weeks" In order to avoid conflict with chemotherapy, each cycle of immunotherapy can be delayed: *see the study schema*).

1. Physical examination will be performed by the investigator/sub-investigator or their designee.
2. Vital signs (temperature, blood pressure, pulse rate, and respiratory rate) will be performed before (within 30 minutes) and after (within 30 minutes) intra-nodal vaccine doses.
3. Pregnancy test is only for WOCBP who are sexually active. Test prior to cycle 1 is to be done on day 1 and must be resulted prior to vaccination.
4. Glucose, BUN, creatinine, sodium, potassium, chloride, CO₂, calcium, total protein, albumin, alkaline phosphatase, AST, ALT, total bilirubin, amylase, lipase.
5. Celecoxib will be administered orally, at a dose of 200 mg, twice daily on vaccine and CKM study treatment days
6. Peripheral blood for potential correlative studies will be collected at the following time points: once during the pre-screening, within 60 minutes before the vaccinations of the priming cycle, and booster cycles 1 and 2; and within 60 minutes after completing booster cycle 2 on Friday. Peripheral blood for potential correlative studies may additionally be drawn within 60 minutes before the vaccination of booster cycle 3 on Monday and within 60 minutes after completing booster cycles 1 and 3 on Friday.
7. Performed within 2 weeks prior to the priming dose of vaccine and 5 business days prior to cycles 1, 2 and 3 vaccines.
8. CT or MRI imaging should be performed prior to cycle 1 if the recovery period from surgery is greater than 6 weeks.
9. At the discretion of the treating physician, the tests/procedures due to be performed at the Off Study Treatment visit may be performed on the last day of the CKM treatment for scheduling purposes.
10. Performed as routine pre-operative evaluation.
11. AEs /conmeds should be collected up to 5 days after treatment, unless considered clinically significant or serious in nature in which case they will be followed until resolution or Grade 1.

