Dose escalation will start with dose tier 1 and proceed to dose tier 2 in the absence of RLTs. Otherwise the dose will be de-escalated to tier -1. The escalation/de-escalation schema uses the following table. Under this schema, more than one patient can be enrolled at the same time; however, *within Phase 1, CKM cannot be started on the next patient until the previous patient completes the cycle of CKM and an additional one week of observation for potential RLTs (total of two week difference between the consecutive patients). Also, CKM cannot be started on the next dose until 2 patients on the lower dose complete the CKM regimen and additional one week of observation for potential RLTs.* Similar rule will be applied during the escalation between different tiers and for the patients within the same dose tier, in order to allow time to evaluate any potential toxicities.

The establishment of the RP2D will be based on an adaptive design for which the next dose will be set according the following rules:

Dose Escalation/De-escalation Rules

Observed Number of RLTs on a Dose Tier	Decision Rule for the Next Subject
There is at least 1 RLT among the last 2 subjects treated on this dose tier and the proportion of DLTs on this dose tier is > 0.30	Assign to next lower dose
There are no RLTs among the last 2 subjects treated on this dose tier and the proportion of RLTs among all subjects on this dose tier is ≤ 0.30	Assign to next higher dose
Neither of the above is satisfied	Assign to the same dose

If no RLTs are observed among the first 3 dose tiers, four additional patients will be added to tier 3 for a total of 6 on tier 3. If, after treating 10 patients without RLT (2 + 2 + 6), dose tier 3 will be declared the RP2D. If an RLT is observed at any dose tier the adaptive up-and-down design will commence until 15 patients are observed after which the Phase 2 starting dose will be estimated by isotonic regression.

Regimen limiting toxicities (RLTs) are defined as the following toxicities:

Vaccine possibly, probably or definitely related RLTs

- Grade 2 or more bronchospasm or generalized urticaria (hypersensitivity)
- Grade 2 or more allergic reaction
- Grade 3 injection site reaction due to vaccine
- > Grade 3 toxicity of any kind related to the DC vaccine

CKM possibly, probably or definitely related RLTs

- Grade ≥ 3 leukopenia or neutropenia persisting ≥ 4 days (96 hours) after treatment

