- Greater than or equal to grade 3 non-hematologic adverse events, except for the following grade 3 toxicities unless they last greater than one week:
 - Flu-like symptoms/constitutional symptoms (i.e., fever, chills, arthralgias, myalgias)
 - Depression, anxiety, restlessness, or insomnia
 - Manageable GI symptoms (i.e., nausea, diarrhea)

The observation period for each patient in the Phase 1 portion of this study will be up to 5 weeks (i.e. up to and including the Friday 1 week after the end of the chemokine modulating regimen).

Note: The last 2 patients in the Phase 1 cohort that determines the RP2D will continue on to the Phase 2 part of the trial and will receive the 2nd and 3rd booster/CKM cycles and follow-up per the Phase 2 portion of this protocol. All patients in the dose finding cohort will be followed for primary efficacy endpoints as well as have blood and serum drawn for corollary studies.

Patients in the Phase 1 (safety) cohort will receive their study treatment and will be monitored for RLTs according to the following timeline:

Eligibility	ECOG performance status, blood work CRS + HIPEC
Screening	History and physical exam, ECOG performance status, blood work, and evaluation of tumor material
Post-surgery (after the discharge from the hospital)	Leukapheresis
Week 1* (upon recovery from surgery; at least 4 weeks after surgery)	Priming Vaccine dose; no chemokine modulation Monday: α DC1 vaccine Oral celecoxib, 200 mg, twice daily on the day of vaccination Tues – Sun: oral celecoxib 200mg, once daily
Weeks 2-3	Rest – continue oral celecoxib, 200 mg, once daily
Week 4	Cycle 1 (“booster cycle”) Monday: α DC1 vaccine Tues – Fri: Systemic Chemokine Modulation Regimen. Oral celecoxib, 200 mg, twice daily on the days of vaccination and CKM. Celecoxib will be discontinued after CKM on Friday. Rintatolimod is only administered on Wednesday and Friday.
Off study treatment	Follow-up for Time-to-Progression/occurrence (TTP)

CRS: Cytoreductive surgery; HIPEC: Hyperthermic intraperitoneal chemoperfusion; TTP: Time-to-progression

*Adjuvant immunotherapy may be delayed until full recovery at the discretion of the investigator/sub-investigator. The beginning of immunotherapy will be considered week 1 of the experimental treatment and the timing of all subsequent elements of treatment will be based upon the first vaccine.

5.2 Phase 2: Efficacy assessment of α DC1 vaccine followed by the chemokine-modulatory regimen (CKM)

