5.8 Off Study Treatment Visit

Within 1-2 weeks after the last day of study treatment, patients will have their last study specific clinical visit. At the discretion of the treating physician, the tests/procedures due to be performed at the Off Study Treatment visit may be performed on the last day of the CKM treatment for scheduling purposes.

AEs and conmeds will be collected for up to 5 days post last dose of treatment. Any patient experiencing study related SAE will be followed until resolution to Grade 1 or baseline.

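### No CBC or chemistry is scheduled between the start of CKM and the close of the Phase 1 RLT window, or after booster 3, so an asymptomatic laboratory RLT can go uncounted

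*Combined protocol and SAP*

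**What the plan says.** - **RLT definition (5.1).** The CKM list includes grade 3 or higher "leukopenia or neutropenia persisting" 96 hours or more after treatment. It also counts most grade 3 or higher non-haematologic events, which can be laboratory-only.
- **Observation (5.1).** The Phase 1 window runs "up to and including the Friday 1 week after the end of the chemokine modulating regimen". The next patient's CKM waits until the previous patient "completes the cycle of CKM and an additional one week of observation for potential RLTs".
- **Decision (5.1).** No RLT in 10 patients (2 + 2 + 6) makes tier 3 the RP2D. Otherwise: "If an RLT is observed at any dose tier the adaptive up-and-down design will commence until 15 patients are observed", followed by isotonic regression.
- **Exposure.** A Phase 1 patient receives one booster/CKM cycle, with one exception in 5.1: "The last 2 patients in the Phase 1 cohort that determines the RP2D will continue on to the Phase 2 part of the trial".
- **Laboratory tests (10).** CBC and chemistries are marked at screening, priming and the three boosters. Footnote 7 fixes their timing: "Performed within 2 weeks prior to the priming dose of vaccine and 5 business days prior to cycles 1, 2 and 3 vaccines". The off-treatment column has adverse events, CEA and imaging only.
- **Off-treatment visit (5.8).** It falls "Within 1-2 weeks after the last day of study treatment", but its tests "may be performed on the last day of the CKM treatment for scheduling purposes".
- **Other blood (10, footnote 6).** The Friday sample at the end of CKM is for correlative studies. It is required after booster 2 and optional after boosters 1 and 3.

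**The concern.** The plan reserves a week to watch for RLTs and lets single events steer dosing. Yet for one of its named RLTs it schedules no test that could reveal the event. The error runs one way, because a missed RLT can only make the regimen look safer. Lowered white count is a listed interferon risk (7.1.3), and interferon is the drug being escalated. Footnote 7 also governs chemistries, so a laboratory-only grade 3 event such as raised transaminases falls into the same gap. In Phase 2 the RLT count drives the suspension rule in 13.4.

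What can be missed is mainly asymptomatic. Clinical RLTs would be seen, and serious consequences such as infection would reach the monthly DSMB and the DSMC, which can suspend accrual (12.1).

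**Working it through.** **1. Day count.** Take the last CKM dose (Friday) as day 0. The booster Monday is then day −4 and CKM starts on day −3. Footnote 7 is read as within 5 business days before the vaccine.

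| Event | Day |
|---|---|
| Count before booster 1 | −11 to −4 |
| Friday correlative sample | 0 |
| 96 hours after treatment | 4 |
| Routine AE collection ends (5.8) | 5 |
| Phase 1 RLT window closes | 7 |
| Off-treatment visit, no CBC | 7 to 14, or 0 if moved |
| Count before booster 2, 4-week target (−4 + 28 = 24) | 17 to 24 |
| Count before booster 2, 12-week limit (−4 + 84 = 80) | 73 to 80 |

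Scheduled counts from day −3 to day 7: none. Scheduled counts after booster 3: none.

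**2. Patients with no later count.** Only the last 2 Phase 1 patients go on to booster 2. So 10 − 2 = 8 of 10 (no-RLT path), or 15 − 2 = 13 of 15 (up-and-down path), have no scheduled count after their only CKM cycle.

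**3. What one missed tier-3 event changes.** Apply the 5.1 rules to 15 patients, with one RLT at tier 3 and no other. The first four patients are 2 at tier 1 and 2 at tier 2.

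- RLT in the 1st tier-3 patient: 1/1 exceeds 0.30, so down to tier 2. No RLT there, so back up. At 1/2 with the RLT among the last two, down again, then up. At 1/3 with no RLT in the last two, stay. From 1/4 onward, stay at the top tier. Totals: 2, 4 and 9 patients.
- RLT in the 2nd: two step-downs again, so 9 at tier 3.
- RLT in the 3rd: 1/3 gives one step-down. The next patient makes it 1/4, so stay. Total 10 at tier 3.
- RLT in the 4th, 5th or 6th: 1/4, 1/5 and 1/6 are all at or below 0.30, so no step-down. Total 11 at tier 3.

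Tier 3 therefore ends at 1/9 = 0.11, 1/9 = 0.11, 1/10 = 0.10 or 1/11 = 0.09. All are well below the 30% that 13.4 names as the dose-finding target. Lower tiers have no RLT, so isotonic regression leaves these values unchanged. Seeing the event adds 15 − 10 = 5 patients, and tier 3 still qualifies.

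This trace covers tier 3. A lone tier-1 RLT would route through tier −1, and the footnote to the dose table then keeps rintatolimod at 100 mg in later cohorts. The conclusion is not extended to that case.

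**4. Section 13.4.** The posterior is 1 − BetaCDF(0.30; 1.93 + r, 4.74 + n − r).

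- n = 10, r = 5: Beta(6.93, 9.74) gives 0.831, with binomial tail 0.150.
- n = 168, r = 56: Beta(57.93, 116.74) gives 0.812, with tail 0.194.

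Both match the plan. All 22 rows reproduce, and one RLT fewer gives a posterior below 0.80 in each. The boundaries are right. The weakness is in r, the count fed into them. Phase 2 states no RLT cut-off, so a cytopenia still present before booster 2 or 3 can be scored, but one that clears sooner cannot. Chemotherapy, allowed from 5 days after a cycle (5.2), would confuse attribution of a late count. After booster 3 there is no later count at all.

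**The case against.** The strongest reply concerns consequence. A reader might infer that one unseen cytopenia produces the wrong RP2D. The documents do not support that: by step 3 a lone tier-3 event changes the path and the number of patients, not the choice of tier 3. Nor can a haematologic RLT rate be assumed to show harm. None is given, and any rate below 30% would leave tier 3 acceptable. This part of the reply stands.

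Prior experience also counts. A similar CKM trial used the same interferon ladder (5, 10 and 20 MU/m²) with rintatolimod daily rather than every second day. It finished phase I without RLTs and went on at 20 MU/m² (2.6.3). Section 7.1.4 reports no dose-limiting haematologic toxicity with rintatolimod, and good tolerance with interferon at lower doses. This lowers the concern but does not remove it. That trial's laboratory schedule is not shown, no vaccine is mentioned, and the present protocol keeps the RLT on its list.

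Other provisions help only in part. Related toxicities are followed to grade 1 or baseline (7), toxicities are evaluated as they arise (12.1), and adverse events must resolve before adjuvant chemotherapy (6.2). Investigators may also order counts. None of these requires one.

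Finally, the ±1 week window in section 10 covers both treatment and procedures. Moving booster 2 a week early puts the count at days 10 to 17. Moving the count a further week early puts it at days 3 to 10. So an early count is possible for patients who receive booster 2, but only by discretion, and never for the other Phase 1 patients.

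**Conclusion.** The scheduling gap is plain on the text and should be fixed. A stated RLT has no scheduled test in the Phase 1 window or after booster 3, and any resulting error makes the regimen look safer.

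Its size is modest. One missed tier-3 RLT skips the up-and-down stage and 5 patients. The choice of tier 3 is threatened only if several RLTs occur and go unseen. The undercount, in Phase 1 or in 13.4, cannot be sized without a haematologic RLT rate. A reader might also infer that patients are left without safety monitoring; they are not, since symptomatic toxicity remains visible and reviewed.

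The conclusion assumes that a tier qualifies when its estimated RLT rate is at or below 30%, as 5.1 states no separate selection rule. It also assumes no other RLT in the traced cases. The documents do not say whether Phase 1 is complete; if it is, the gap after booster 3 and the partial Phase 2 gap remain.

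**What to change.** Amend the calendar and 5.8:

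- Add CBC with differential and chemistries to the off-treatment visit, drawn between 96 hours and 7 days after the last CKM dose. Day 7 is best, because it lies in both the Phase 1 RLT window and the existing visit window.
- Apply this to every Phase 1 patient after booster 1, including the 2 who continue, and to Phase 2 patients after booster 3.
- Exempt these tests from the last-CKM-day option and the ±1 week window.
- Score CKM-related grade 3 or higher leukopenia or neutropenia at that draw as meeting the existing 96-hour RLT, and follow it to grade 1 or baseline. The draw is already past 96 hours after treatment, so no further hold to prove persistence is needed.
- State that the result is recorded even though routine AE collection stops at day 5.

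A CBC before adjuvant chemotherapy after boosters 1 and 2 in Phase 2 is a secondary, optional addition. It would also check the resolution rule in 6.2. The RLT definition and the 13.4 boundaries need no change.

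The cost is a less flexible visit date and a few routine draws, with a possible extra trip for the 2 continuing Phase 1 patients. A cytopenia that clears before the draw can still be missed.
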